4.5. Other Safety Considerations

The current clinical experience of CBP-201 is limited. Given that dupilumab is a similar product that has been marketed and binds to the same target (IL-4R α), examples of existing safety observations include but are not limited to the following:

- Hypersensitivity reactions (e.g., urticaria, rash, erythema nodosa, immediate severe allergic reactions, serum sickness);
- Eosinophilic disease (e.g., systemic eosinophilia, sometimes manifested as eosinophilic pneumonia or clinical features of vasculitis consistent with eosinophilic granulomatous polyangiitis, worsening of pulmonary symptoms, cardiac complications and/or neuropathy in patients with eosinophilia);
- Reactions caused by reduced doses of glucocorticoids (abrupt discontinuation of systemic, local or inhaled glucocorticoids may be related to systemic withdrawal symptoms and/or the appearance of symptoms previously suppressed by systemic

glucocorticoid therapy);

- Injection site reactions;
- Oropharyngeal pain;
- Eosinophilia;
- Conjunctivitis, including allergic conjunctivitis, bacterial conjunctivitis, viral conjunctivitis, giant papillary conjunctivitis, eye irritation and eye inflammation;
- Blepharitis;
- Oral herpes;
- Keratitis, including ulcerative keratitis, allergic keratitis, atopic keratoconjunctivitis and ocular herpes simplex;
- Itchy eyes;
- Other herpes simplex virus infections, including genital herpes, herpes simplex otitis externa and herpes virus infections;
- Dry eye;
- Joint pain;
- Gastritis;
- Insomnia;
- Toothache.

4.6. Study Rationale

As mentioned above, it can be seen from the results of Phase Ia and Ib clinical studies completed in Australia and New Zealand that in healthy subjects, a single subcutaneous injection of CBP-201 75 mg, 150 mg, 300 mg and 600 mg and intravenous injection of 300 mg or subcutaneous injections of 75 mg, 150 mg and 300 mg once a week for 4 times in patients with moderate to severe AD have good safety and tolerability. At the same time, in patients with moderate to severe AD, CBP-201 150 mg and 300 mg injected subcutaneously every week demonstrated preliminary clinical efficacy, and the changes in TARC, a biomarker related to AD severity, showed a consistent trend with the improvement of the disease. At the same time, there was no significant difference in TEAEs between each dose group and the placebo group. These study results support further research on the therapeutic effects of CBP-201 on AD. At the same time, the ongoing Phase I study of a single subcutaneous injection of CBP-201 150 mg, 300 mg and 600 mg in healthy Chinese subjects has completed enrollment and follow-up, and at three blinded safety review committee meetings conducted 15 days after the administration in each dose group, the investigators all believed that CBP-201 was safe and well tolerated, supporting the continued clinical development of CBP-201 in China. Therefore,

this study is planned to further assess the efficacy, safety and PK characteristics of CBP-201 in patients with moderate to severe AD in China.

Compared with adults, the prevalence of AD is significantly higher in children and adolescents [1,2,4], and the treatment options available for children and adolescents aged 12 years and above are more limited. For children with moderate to severe AD, in particular, there is still a huge unmet clinical need. CBP-201 has demonstrated good safety, tolerability and efficacy in previously completed clinical studies, and the marketed same-target (IL-4R α) product dupilumab has been approved by the U.S. Food and Drug Administration (FDA) and the European Medicines Agency (EMA) for the treatment of moderate to severe AD in children aged 6-11 years and adolescents aged 12 years and above, and also been approved in China for the treatment of moderate to severe AD in adolescents aged 12 years and above. The safety and efficacy data of dupilumab in pediatric AD patients have provided strong support for the rationality and feasibility of clinical studies of CBP-201 in the pediatric population, that is, no unique pediatric safety issues have been observed with the marketed medicinal product of the same class sharing the same target as CBP-201 (IL-4R α), and the efficacy in the pediatric population is definite. In order to encourage and facilitate the research and development of medicinal products for the pediatric population, the International Council for Harmonization of Technical Requirements for Pharmaceuticals for Human Use (ICH) has formulated ICH E11 (R1), a specific guideline for the clinical studies of medicinal products for the pediatric population (including adolescents aged 12 years and above). With regard to the timing of the initiation of pediatric studies during the research and development of a medicinal product, ICH E11 (R1) recommends that factors such as the medicinal product, the type of disease being treated, safety considerations, and the efficacy and safety of alternative treatments should be comprehensively considered. In cases where the medicinal product will be used in pediatric patients but the disease to be treated is not urgent, ICH E11 (R1) recommends that testing of these medicinal products in pediatric populations can usually begin at clinical phase 2 or 3 (Section 2.3.3). For medicinal products intended to treat serious or life-threatening diseases, occurring in both adults and pediatric patients, for which there are currently no or limited therapeutic options, ICH E11 (R1) recommends that medicinal product development should begin early in pediatric population, following assessment of initial safety data and reasonable evidence of potential benefit (Section 2.3.2). In conclusion, this study plans to enroll certain number of adolescents with moderate to severe AD aged 12 years and above under the premise of meeting the requirements of the ICH E11 (R1) guideline. The safety and efficacy data of adolescent AD patients obtained in this study will provide an important reference for further design and conduct of clinical studies in younger pediatric populations in the future.

The treatment in this study is divided into two stages. Stage 1 is a placebo-controlled design (subjects will receive CBP-201 600 mg or placebo SC administration on D1, and start to receive CBP-201 300 mg or placebo administration Q2W starting from Week 2); Stage 2 is the maintenance treatment period with different dosing regimens of CBP-201 (CBP-201 300 mg,

Q2W or Q4W).

5. Study Objectives

5.1. Primary Objective

- To assess the efficacy of CBP-201 in subjects with moderate to severe AD

5.2. Secondary Objectives

- To assess the safety and tolerability of CBP-201 in subjects with moderate to severe AD
- To assess the PK characteristics of CBP-201 in subjects with moderate to severe AD
- To assess the PD characteristics of CBP-201
- To assess the immunogenicity of CBP-201

6. Study Plan

6.1. Overall Study Design and Plan

This study is a randomized, double-blind, multi-center, controlled study designed to assess the efficacy, safety and PK characteristics of CBP-201 in eligible subjects with moderate to severe AD.

The study includes a screening period, a treatment period and a follow-up period. The treatment period is divided into two stages:

Stage 1 study: It is a placebo-controlled study, in which subjects who meet the inclusion criteria and do not meet the exclusion criteria will be stratified according to the severity of their baseline disease (moderate [IGA=3] and severe [IGA=4]) and randomized into one of the following 2 groups to receive investigational product or placebo treatment by the ratio of 2:1:

- Group A (CBP-201): the subjects will receive a subcutaneous injection of CBP-201 600 mg (4 ml in total, 2 injections of 2ml each in different sites) on Day 1, begin to receive a subcutaneous injection of CBP-201 300 mg (2 ml) from Week 2 (W2), and receive treatment at the same dose every 2 weeks thereafter until W14;
- Group B (placebo): the subjects will receive a subcutaneous injection of placebo 4 ml (2 injections of 2ml each in different sites), begin to receive a subcutaneous injection of placebo 2 ml from W2, and receive placebo 2 ml every 2 weeks thereafter until W14.

The grouped dosing regimen in Stage 1 is shown in the table below:

Table 6.1 Grouped Dosing Regimen in Stage 1

Group	W0	W2	W4	W6	W8	W10	W12	W14
Group A	4XC	2XC						
Group B	4XP	2XP						

Note: C=CBP-201; P=placebo; #X=number of ampoules

Before the administration of study drug at W16 visit, all subjects will be assessed for efficacy, and treatment assignment for Stage 2 maintenance treatment is based on whether a subject achieves a 50% or greater reduction in EASI score (ie EASI-50).

Stage 2 study: The grouping for Stage 2 maintenance treatment is as follows:

- Subjects who have achieved EASI-50 in the W16 pre-administration treatment assessment will be 1:1 randomized to one of the following two groups to receive study treatment starting from W16:
 - Group C: The subjects will receive a subcutaneous injection of CBP-201 300 mg every 2 weeks until W50;
 - Group D: The subjects will receive a subcutaneous injection of CBP-201 300 mg every 4 weeks. In order to maintain the injection every 2 weeks blind, when not

receiving CBP-201, the subjects will receive an injection of placebo 2 ml once every 4 weeks until W50.

- Subjects who have not achieved EASI-50 in the W16 pre-administration treatment assessment will receive the following treatment starting from W16:
 - Group E: The subjects will receive a subcutaneous injection of CBP-201 300 mg every 2 weeks until W50.
 - If subjects in group C and group D have not achieved EASI-50 in two continuous pre-administration treatment assessments, they will be assigned to group E to be treated with subcutaneous injection of CBP-201 300 mg every 2 weeks from the visit when EASI-50 is not achieved for the second time to W50.

The grouped dosing regimen in Stage 2 is shown in the table below:

Table 6.2 Grouped Dosing Regimen in Stage 2

Group	W16	W18	W20	W22	W24	W50
Group C	2XC	2XC	2XC	2XC	2XC	2XC
Group D	2XC	2XP	2XC	2XP	2XC	2XP
Group E	2XC	2XC	2XC	2XC	2XC	2XC

Note: C=CBP-201; P=placebo; #X=number of ampoules

During the study period, subjects must apply a mild emollient to the AD-affected area at least twice a day as background treatment (but should avoid using emollients within 4 hours before AD assessment at each visit).

All subjects (including the subjects who are early terminated of the treatment) will be followed up for 8 weeks after the last dose.

In this study, an independent DSMB will be established to regularly review and evaluate the cumulative study data, to guarantee the safety of subjects, implementation and progress of the study, and to give the sponsor a suggestion on whether to continue the study.

The overall study design is shown in [Figure 1](#).

6.2. Study Steps

The study consists of a screening period, a treatment period (including Stage 1 treatment [16 weeks] and Stage 2 maintenance treatment [36 weeks] and a follow-up period (8 weeks).

After signing the ICF, subjects will be assessed for study eligibility at the screening visit within 28 days prior to the baseline visit. Before D1 administration of study drug, subjects who were eligible at the screening visit will be confirmed again for their eligibility. After baseline assessment, the subjects who are confirmed to meet the inclusion criteria will be randomized to Group A (CBP-201) or Group B (placebo) in a 2:1 ratio to receive CBP-201 or placebo SC administration. Vital signs monitoring will be conducted at the study site before D1, W2 and W4 administration and 2 hours after administration, and before and 30 minutes after each

administration from W6 to W14.

Before W16 administration, the therapeutic results of all subjects will be assessed, and treatment assignment for Stage 2 maintenance treatment is based on whether a subject achieves a 50% or greater reduction in EASI score (ie EASI-50). Subjects who are assessed to have achieved EASI-50 before W16 administration will be 1:1 randomized to Group C or Group D and start receiving SC administration of CBP-201 300 mg Q2W or Q4W until W50 (*If subjects in group C and group D have not achieved EASI-50 in two continuous pre-administration treatment assessments, they will be assigned to group E to be treated with subcutaneous injection of CBP-201 300 mg every 2 weeks from the visit when EASI-50 is not achieved for the second time to W50.*); subjects who are assessed to have not achieved EASI-50 before W16 administration will be assigned to Group E to start receiving SC administration of CBP-201 300 mg Q2W until W50. All subjects should undergo vital signs monitoring before administration and 2 h after administration at W16, W18 and W20 at the study site, and before and 30 min after each administration from W22 to W50. After the end of Stage 2 (W52), subjects will be followed up for safety and efficacy for 8 weeks to further explore the PK and PD characteristics of CBP-201.

Subjects will return to the study site for examinations and assessments according to the time specified in the [Study Flow Chart](#). Various study assessments and examinations should be completed before administration at each visit (unless otherwise specified).

Blood samples from all subjects will be collected during the whole study period to evaluate the steady-state PK characteristics of CBP-201 and its PD effects on serum thymus activation regulated chemokine (TARC) level, total immunoglobulin E (IGE) level, peripheral blood eosinophil count and serum IL-4 and IL-13 levels, and to detect ADA (*all ADA positive samples will be further tested for the presence of anti-CBP-201 NAb*).

During the study period, subjects are also required to apply mild emollients to the AD-affected area at least twice a day (in order to facilitate the assessment of dryness and scales, the use of emollients should be avoided within 4 hours before the assessment) and fill in a daily pruritus diary every day. If an intolerable AD recurrence or worsening of the condition occurs, the subject should notify the study site to assess the condition and confirm whether it is necessary to use rescue drugs for treatment.

Throughout the study period, AE assessment will be continued and concomitant medication/treatment information will be collected.

If a subject has ET for any reason, the subject should complete the ET visit within 7 days after ET, and complete the 8-week follow-up visit as much as possible after the ET visit.

The assessment of the severity and impact of AD will be divided into two parts: the investigator's efficacy assessments and the patient reported outcomes:

1) Patient reported outcomes (completed by the subject):

- PP-NRS: It is a single self-reported item designed to measure the peak pruritus or “worst” pruritus in the past 24 hours based on the following questions: “The scores are 0-10, in which 0 represents ‘no pruritus’ and 10 “worst imaginable pruritus”. How do you rate your most severe puritus in the past 24 hours?” [31]. Refer to [Section 17.1, Appendix A](#). The PP-NRS (Daily Pruritus Diary) will be distributed at the beginning of the screening visit. Subjects will be instructed to complete the PP-NRS (Daily Pruritus Diary) within 7 days before the baseline visit (D1) to calculate the baseline average score of subjects, which will be reviewed by the study staff at the baseline visit (D1). Thereafter (from D1), the daily PP-NRS will be collected every day (in the past 24 hours).
- DLQI: It is a questionnaire containing 10 items to assess the impact of AD on quality of life (QOL) in the past week, and the scores range from 0 (no disease) to 30 (severe disease); the higher the score, the worse the quality of life. Refer to [Section 17.2, Appendix B](#). DLQI score will only be assessed among subjects ≥ 16 years, and it will be assessed once a week during the study period.
- POEM: It is a questionnaire composed of 7 items to assess disease symptoms on a scale of 0-4 (dryness, itching, flaking off, cracking, sleeplessness, bleeding and weeping or oozing); the scores range from 0 (no disease) to 28 (severe disease); the higher the score, the worse the quality of life. Refer to [Section 17.3, Appendix C](#). It will be assessed once a week during the study period.

2) Investigator's efficacy assessments (completed by the investigator):

- IGA: The Validated Investigator Global Assessment for AD (vIGA-AD™) Scale is a 5-point classification scale based on the overall appearance of the skin lesions at a specific time point (0=clear; 1=almost clear; 2=mild; 3=moderate; 4=severe). It should be noted that in order to be eligible for selection, the IGA score must be ≥ 3 . See [Section 17.4, Appendix D](#). Please also note that IGA-1 should not contain scales.
- EASI: The EASI scale quantifies the severity and extent of AD, as well as the severity of erythema, infiltration, excoriation and lichenification of the four anatomical regions—head and neck, trunk, upper extremities and lower extremities. The total EASI score ranges from 0 (lowest) to 72 (highest); the higher the score, the higher the severity of AD (more severe). It should be noted that in order to be eligible for selection, the EAS score must be ≥ 16 . See [Section 17.5, Appendix E](#).
- The “Rule of Nines” is used to estimate the maximum percentage of AD-affected BSA in each area: head and neck [9%], anterior trunk [18%], back [18%], upper limbs [18%], lower limbs [36%] and genitals [1%]. The number of palms of AD-affected skin in a body part can be used to determine the extent (%) of AD involvement in that body part. Regardless of the age of the subject, the area of the subject's entire palm (five fingers adducted together) is about 1% of the subject's

BSA. The number of palms in different body parts is assessed to calculate the percentage of BSA affected by AD. It should be noted that in order to be eligible for selection, the percentage of AD-affected BSA must be ≥ 10 . See [Section 17.6, Appendix F](#).

- AD score (SCORAD): It is a clinical tool used to assess the severity of AD (extent/severity) and subjective signs/symptoms (e.g., itch/sleeplessness). The degree of lesions is scored using the “rule of nines” method. The severity is determined by grading the severity of the 6 signs (erythema, edema, oozing/crusting, excoriation, lichenification, and skin dryness) on a 0-3 subscale. The assessment of each sign is scored on the most representative skin lesions. See [Section 17.7, Appendix G](#).

Note: in order to facilitate the assessment of dryness and scales, the use of emollients should be avoided within 4 hours before the assessment of AD.

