12.3. Basis of Sample Size

The sample size of 255 cases (in a 2:1 ratio, 170 cases in the CBP-201 300 mg Q2W group, and 85 cases in the placebo group. Assuming that the dropout rate in the treatment group is 15%, then about 144 cases in the CBP-201 300 mg Q2W group and 72 cases in the placebo group will be able to complete the study) can provide a power of 90% to detect the therapeutic effect on the primary endpoint in the CBP-201 300 mg Q2W group and the placebo group. This power is calculated based on the following assumption: the proportion of subjects reaching the primary efficacy endpoint is 27% in the CBP-201 300 mg Q2W group and 9% in the placebo group, and the significance level for two-sided tests is 0.05.

Based on the results of another conducted phase II international multicenter clinical study of CBP-201 in patients with moderate-to-severe atopic dermatitis, the proportion of subjects reaching the primary efficacy endpoint was 28.1% in the CBP-201 300mg Q2W group and 10.7% in the placebo group, at a two-sided test significance level of 0.05, and if the results of this trial are similar to that of the WW001 trial, the above sample size would provide a power of more than 85% to detect the therapeutic effect on the primary endpoint between the CBP-201 300 mg Q2W group and the placebo group. Therefore, no adjustment is made to the sample size.

The primary analysis of this study will still be based on the 255 subjects enrolled in accordance with V2.1 and its earlier versions of the protocol. Subjects newly enrolled (approximately 81 cases) based on the protocol after V2.1 will not be included in the primary analysis, and only supplementary analysis will be performed.

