					imputation rules of the main estimator, that is, the multiple imputation method (MI) will be used to impute the missing data in the placebo group, and the J2R (jump to reference) method will be used to impute the missing data in the CBP-201 group.
Estimand of key secondary endpoints	
The differences in the following measures in patients aged 12 years and older with moderate to severe AD and weighing ≥ 40 kg between the CBP-201 300mg Q2W group and the placebo group:
 
 • The proportion of subjects achieving EASI-75 at W16; • The proportion of subjects whose weekly average PP-NRS is decreased by ≥ 4 points from baseline at W16; • The proportion of subjects whose weekly average PP-NRS is decreased by ≥ 3 points from baseline at W16; • Change and percentage change in the weekly 	FAS (will include all subjects in Randomization Set 1 who have received the study drug at least once.)	
For subjects who experience intercurrent events, their visits after the intercurrent events will be handled in accordance with the strategies for managing intercurrent events listed in Table 12.1 and Table 12.3.
 
If the target variable is still missing after application of the strategies for managing intercurrent events, the multiple imputation (MI) method will be used to impute the missing data in the placebo group, and the J2R (jump to reference) method will be used to impute the
	
For categorical variables, differences in response rates between the treatment group and placebo group and their 95% confidence intervals will be analyzed using the Cochran-Mantel-Haenszel test stratified by baseline disease severity (IGA 3 or 4).
 
For continuous variables, analysis will be performed using an MMRM model that will include treatment group, baseline disease severity (IGA 3 or 4), baseline value of the corresponding endpoint, visit, interaction of visit and treatment group, and the LSMEAN estimate values and their 95% confidence
	
Sensitivity analysis 1: When the target variable is still missing after application of the strategy for managing intercurrent events, categorical variables will be classified as treatment failure. Continuous variables should be imputed with WOCF.
 
Supplementary Analysis 1: Primary analysis will be performed using the PPS.
 
Supplementary analysis 2: The treatment policy strategy will be used for all intercurrent events; the FAS will be used, and the missing data will be subject to the imputation rules of the main

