Estimand of key secondary endpoints	
The differences in the following measures in patients aged 12 years and older with moderate to severe AD and weighing ≥ 40 kg between the CBP-201 300mg Q2W group and the placebo group:
 
 • The proportion of subjects achieving EASI-75 at W16 • The proportion of subjects whose weekly average PP-NRS is decreased by ≥ 4 points from baseline at W16; • The proportion of subjects whose weekly average PP-NRS is decreased by ≥ 3 points from baseline at W16; 	FAS1 (will include all subjects in RS1 who have received the study drug at least once).	
For subjects who experience intercurrent events, their visits after the intercurrent events will be handled in accordance with the strategies for managing intercurrent events listed in Table 7.4.2.
 
If the target variable is still missing after application of the strategies for managing intercurrent events, the multiple imputation (MI) method will be used to impute the missing data in the placebo group, and the J2R (jump to reference)
	
For categorical variables, differences in response rates between the treatment group and placebo group and their 95% confidence intervals will be analyzed using the Cochran-Mantel-Haenszel test stratified by baseline disease severity (IGA 3 or 4).
 
For continuous variables, analysis will be performed using an MMRM model that will include treatment group, baseline disease severity (IGA 3 or 4), baseline value of the
	
Sensitivity analysis 1: When the target variable is still missing after application of the strategy for managing intercurrent events, categorical variables will be classified as treatment failure. Continuous variables should be imputed with WOCF.
 
Sensitivity analysis 2: For the subjects who are incorrectly stratified and randomized, the analysis will be performed using the stratification during randomization and the method the same as the main estimator;
 
Supplementary analysis 1: The analysis will be performed using the same method as the main estimand based on the PPS1.
 
Supplementary analysis 2: The treatment policy strategy will be used for all intercurrent events; the FAS1 will be used,

Label of estimand	Description of estimand	Main estimator			Sensitivity/ Supplementary analysis
		Analysis sets	Rules for imputation	Model/method for the main analytical methods	

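### The two PP-NRS responder tests are stratified by IGA only and leave out baseline PP-NRS: the tests are valid, but give up a little precision that the collected data could recover

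*Protocol*

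**What the plan says.** Protocol 6.2 has the daily itch diary completed "within 7 days before the baseline visit (D1) to calculate the baseline average score of subjects". Protocol 7.1 sets an entry floor of 4 on the 0 to 10 scale and requires at least four diary days out of seven, so an eligible subject has a baseline value.

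For categorical key secondary endpoints, SAP 7.4.3 specifies the "Cochran-Mantel-Haenszel test stratified by baseline disease severity (IGA 3 or 4") and no other factor. Protocol Table 12.4 says the same. For continuous key secondaries, the MMRM terms include "baseline disease severity (IGA 3 or 4), baseline value of the corresponding endpoint, visit". SAP 7.4.3 also puts the endpoint's baseline value into the imputation model.

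SAP 7.4.3 defines a baseline PP-NRS median split, but uses it only for subgroup analyses of IGA response and EASI-75. Protocol 12.7.4 had foreseen subgroup analyses by baseline characteristics for the key secondaries in general. No sensitivity or supplementary analysis brings baseline PP-NRS into the itch responder comparisons.

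Under Protocol 12.7.1 the testing order is IGA response, EASI-75, PP-NRS drop of at least 4, PP-NRS drop of at least 3, PP-NRS change and percentage change, EASI-90. Randomisation (Protocol 6.3.1) is stratified by IGA only.

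**The concern.** Both responder endpoints are absolute drops, so the definition ties the attainable response to the starting value. IGA is an investigator's skin score and does not measure itch. The plan treats baseline PP-NRS as informative in the MMRM and in the imputation, then omits it from the responder tests of the same variable without giving a reason.

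These two tests are gates. Failing the 4-point test stops formal testing of the 3-point test, PP-NRS change and EASI-90. Failing the 3-point test stops the last two. The documents state power for the IGA endpoint only, so the margin at these gates is unknown and even a small free gain has some value.

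**Working it through.** **1. The plan's own power figure.** Protocol 12.3 randomises 170 to CBP-201 and 85 to placebo, allows 15% dropout (about 144 and 72 completers), tests two-sided at 0.05, and states that this "can provide a power of 90% to detect the therapeutic effect on the primary endpoint". The response rates it assumes are "27% in the CBP-201 300 mg Q2W group and 9% in the placebo group".

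- Pooled rate = (72 × 0.09 + 144 × 0.27)/216 = 0.21
- SE under H0 = √[0.21 × 0.79 × (1/72 + 1/144)] = 0.0588
- SE under H1 = √[0.09 × 0.91/72 + 0.27 × 0.73/144] = 0.0501
- Power = Φ[(0.18 − 1.96 × 0.0588)/0.0501] = Φ(1.29) = 90.2%

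The stated 90% reproduces, but it concerns IGA response. There is no counterpart for itch.

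**2. Why baseline matters by definition.** A subject entering at 4 must reach 0 to be a 4-point responder; one entering at 9 need only reach 5. For the 3-point version the targets are 1 and 6. This makes an association plausible. It does not give its size.

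**3. Change-score simulation (170 v 85).** Assumed, not in the documents: baseline mean 7.2, SD 1.7, truncated to 4–10; residual SD of change 2.1; slope of change on baseline 0 to −0.7. For slopes −0.3 to −0.7, active-arm 4-point response in the lower v upper baseline half runs from 17% v 27% to 16% v 40%. The chance between-arm imbalance has SD about 0.19, so 0.3 points is about 0.3/0.19 = 1.6 SD. Two runs with these inputs gave, for IGA alone against IGA × baseline median:

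- Power change: 0 to +2.3 points in one run (for example 81.4% to 83.7%; at slope 0, 86.6% to 86.6% and 63.4% to 63.0%). In the other, −0.9 to +0.6 at slopes 0 to −0.3 (within simulation error) and +0.8 to +2.9 at slopes −0.5 to −0.7.
- Shift in the risk difference from a 0.3-point imbalance, slopes −0.3 to −0.7: 0.8–2.3 and 1.0–2.4 percentage points unadjusted; at most about 0.6 with the extra stratum.

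**4. Logistic simulation (170 v 85).** Assumed: baseline mean 7.2, SD 1.6, truncated to 4–10; correlation 0.2 with IGA; placebo/active rates 10/25%, 15/32% and 20/38%; odds ratio (OR) per PP-NRS point 1.0 to 2.0. With no treatment effect (20% in both arms), the IGA-only CMH rejected in 4.7% to 5.2% of trials. Across all settings, mean bias in the rate difference stayed within 0.2 points. Ranges below are over the three rate pairs; the last column is 0.3 × the regression slope of the observed difference on the imbalance.

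| OR per point | Power, IGA only | Gain, IGA × median | Gain, logistic with continuous baseline | Shift per 0.3-point imbalance |
|---|---|---|---|---|
| 1.0 | 84.8–85.3% | −0.3 to −0.2 | −0.6 to −0.3 | about 0 |
| 1.22 | 84.4–85.2% | +0.2 to +0.4 | −0.5 to +0.9 | 0.6–1.2 pts |
| 1.49 | 84.2–84.8% | +0.3 to +1.2 | −0.1 to +2.0 | 1.1–2.1 pts |
| 2.01 | 84.7–85.6% | +2.1 to +2.9 | +3.4 to +4.9 | 2.4–3.3 pts |

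So the figure of about 5 points needs both the strongest association tried and a continuous covariate. The median split itself gains at most about 3.

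**5. Scale of the shift.** At 25% v 10%, the SE of the risk difference is √[0.25 × 0.75/170 + 0.10 × 0.90/85] = 4.6 points. A shift of 1 to 2.4 points is therefore about 0.2 to 0.5 SE.

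**The case against.** The strongest reply is that nothing here is wrong. Stratifying the test by the randomisation factor is a coherent choice, and the simulated error rate is about 5%. A reader might infer that an unadjusted itch imbalance biases the two gatekeeping tests, or that nothing in the design balances itch. Neither holds. Randomisation balances baseline itch in expectation, and chance imbalance is sampling variation that the test's error rate already covers. It moves one trial's estimate conditionally; it does not bias the comparison.

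It is also fair that the gain is small, can be nil, and depends on a prognostic strength the documents do not give. The simulations include no dropout or intercurrent events. Scoring some events as non-response and using jump-to-reference for others could weaken the link between baseline itch and response.

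Timing matters too. Protocol 12.5 unblinds the W16 data at the primary analysis. SAP version 1.0 is dated 20 September 2022, and the later SAP text (Section 6) reports a data review for the final analysis on 18 October 2023. No unblinding date is stated, but replacing the confirmatory test in that later text could well be post hoc.

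What remains is that a collected baseline, already used for the continuous version of the endpoint, is left out of the responder tests without a stated reason.

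**Conclusion.** This holds as a modest efficiency and consistency point, not as an error in the plan. The IGA-only CMH tests of the two PP-NRS responder endpoints are valid and unbiased. They forgo about 0 to 3 points of power relative to a median-split stratum, or up to about 5 relative to a continuous covariate when the odds ratio per point is about 2. They also leave a 0.3-point chance imbalance free to move the risk difference by about 1 to 2.4 percentage points at change-score slopes −0.3 to −0.7, and by up to 3.3 in the strongest logistic setting.

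All these sizes rest on an assumed baseline distribution, responder rates and prognostic strength, with complete data on 170 v 85. If baseline PP-NRS is not prognostic there is nothing to gain. The documents do not support the stronger inference that a result from the planned tests would be unreliable.

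**What to change.** In SAP 7.4.3 and Protocol Table 12.4, for the PP-NRS drops of at least 4 and at least 3 points only, specify the CMH test and Mantel-Haenszel risk difference stratified by IGA (3/4) crossed with baseline weekly average PP-NRS (below the median v at or above it, the split SAP 7.4.3 already defines). The effect measure stays a risk difference.

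If this is fixed before the W16 data are unblinded, make it the main method. If not, keep the IGA-only CMH as the test in the fixed sequence and report the four-stratum version as a labelled supportive analysis. State whether the median found in the 255 subjects is carried into the all-subject supplementary analysis, because a recomputed sample median may differ.

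The cost is a line of SAP text and four strata instead of two: on average 170/4 ≈ 42 active and 85/4 ≈ 21 placebo subjects per stratum, with actual sizes depending on the IGA split. There is no gain if baseline itch proves unrelated to response.
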